7.1.1 Molecular pre-screening

Molecular pre-screening is not required to fulfill the inclusion criteria. If patients have undergone genetic testing for TSC in the course of their routine care this information can be used to confirm the TSC diagnosis (refer to [Table 7-2](#)).

7.1.2 Screening

After signing the study ICF, the screening assessments will be done within 1 to 28 days prior to Day 1 (see [Table 7-1](#) for list of assessments to be performed). All inclusion and exclusion criteria will be evaluated and the investigator verifies that all patients have a clinically definite diagnosis of TSC according to the criteria described below.

Clinically definite diagnosis of TSC

All patients should have a clinically definite diagnosis of TSC according to the updated diagnostic criteria for TSC 2012 (Holpe Northrup, Darcy A. Krueger on behalf of the international TSC consensus (Hyman 2013) to be eligible. Clinically definite diagnosis of tuberous sclerosis according to the updated criteria is defined as either of the following:

- Two major features or one major feature with ≥ 2 minor features from [Table 7-2](#).
- Genetic diagnostic criteria: The identification of either a TSC1 or TSC2 pathogenic mutation in DNA from normal tissue is sufficient to make a definite diagnosis of TSC. A pathogenic mutation is defined as a mutation that clearly inactivates the function of the TSC1 or TSC2 proteins, prevents protein synthesis, or is a missense mutation whose effect on protein function has been established by functional assessment. Other TSC1 or TSC2 variants whose effect on function is less certain do not meet these criteria, and are not sufficient to make a definite diagnosis of TSC.

Note: In this study TSC genetic testing is not mandated. Patients who don't meet criteria in [Table 7-2](#) can be regarded as fulfilling TSC diagnosis criteria if previous TSC1 or TSC2 pathogenic mutation is documented in medical history.

Table 7-2 Diagnostic criteria for Tuberous Sclerosis Complex

Major Features
1. Hypomelanotic macules (≥ 3 , at least 5-mm diameter)
2. Angiofibromas (≥ 3) or fibrous cephalic plaque
3. Ungual fibromas (≥ 2)
4. Shagreen patch
5. Multiple retinal hamartomas
6. Cortical dysplasias ^a
7. Subependymal nodules
8. Subependymal giant cell astrocytoma
9. Cardiac rhabdomyoma
10. Lymphangiomyomatosis (LAM) ^b
11. Angiomyolipomas (≥ 2) ^b

Minor Features

1. "Confetti" skin lesions2. Dental enamel pits (>3)3. Intraoral fibromas (_2)4. Retinal achromic patch5. Multiple renal cysts6. Nonrenal hamartomas

^a Includes tubers and cerebral white matter radial migration lines.
 
^b A combination of the two major clinical features (LAM and angiomyolipoma) without other features does not meet criteria for a definite diagnosis.

Screening for hepatitis B and C

At screening all patients have to be tested for hepatitis B viral load and serologic markers, that is, HBV-DNA, HBsAg, HBs Ab, and HBc Ab. Additionally, all patients have to be tested for hepatitis C using quantitative RNA-PCR.

Please note that patients who test negative for HBV-DNA, HBsAg, and HBcAb but positive for HBs Ab, due to prior history of vaccination against Hepatitis B will be eligible. The fact that the patient had been vaccinated should be entered into the patient's Medical History CRF.

Patients with serological markers indicative of chronic hepatitis B infection or measurable hepatitis C RNA will be excluded from the study.

Electrocardiogram (ECG)

A standard 12-lead ECG is to be performed at screening. Tracings must be dated and signed by the investigator (or his/her designee) and filed with the subject's source documentation. Results from 12-lead ECG should be captured on the ECG Evaluation CRF. Significant findings must be recorded as Relevant Medical History.

Additional, unscheduled, safety ECGs may be repeated at the discretion of the investigator at any time during the study as clinically indicated. Unscheduled ECGs with clinically significant findings should be collected in triplicate. ECG assessments may also be performed at any time during the study at the discretion of the investigator.

Paper ECGs should be labeled with the study number, patient initials (where regulations permit), patient number, date and time and be kept in the source documents at the study site.

Rescreening

Reassessment of any screening criteria is permitted once for previously screen failed patients.

In this case the Subject Number assigned to the patient will not be used and the patient will be assigned a new 7 digit subject number. If the patient has been enrolled and treated, re-screening of the patient is **not** allowed.

In case rescreening occurs, all evaluations re-assessed should meet the eligibility criteria. A new informed consent form must be signed only if there is an interruption in the patient's eligibility evaluation and the investigator chooses to re-screen the patient following screen failure; the 28 day screen period does not apply to the informed consent process. If a new informed consent form is signed, AEs and medical history will be assessed relative to the new

informed consent date. Patients who did not have the required AML lesion size would need to wait at least 3 months before re-screening. For laboratory evaluations used to determine eligibility, a repeated evaluation within the screening window is permitted for screening results out of the defined range before screen failing the patient. If the repeated laboratory result meets the criteria, that result may be used to determine eligibility. If the repeated laboratory result does not meet the criteria, the patient will be considered a screening failure. For details of assessments see [Table 7-1](#).

7.1.2.1 Eligibility screening

The investigator is responsible to ensure only subjects who meet all inclusion and do not meet any exclusion criteria are included in the study.

7.1.2.2 Information to be collected on screening failures

Subjects who signed an Informed Consent Form but failed to be started on treatment for any reason will be considered screen failures. Subjects who are found not eligible after signing the study consent will also be considered as screening failures. The screening failure will be entered on the Disposition Page.

The subject ID, visit date, subject status-screening, demographic information, informed consent, Inclusion/Exclusion and Disposition pages must also be completed for Screen Failure subjects. No other data will be entered into the clinical database for subjects who are screen failures, unless the subject experienced a Serious Adverse Event during the Screening Phase (see Section 8 for SAE reporting details). If a screen failure patient experiences an AE which does not meet the SAE criteria, details about the AE will be recorded only in the investigator's source documents. In case of an SAE after signing of main study informed consent, data must be recorded on both the AE and SAE forms.

7.1.2.3 Patient demographics and other baseline characteristics

During the Screening visit data will be collected on patient characteristics including demographic information (age, sex, race) and other background or relevant medical history (TSC diagnosis, prior anti-angiomyolipoma and TSC therapies), hepatitis and HIV history and any other assessments that are done for the purpose of determining eligibility for inclusion in the study (i.e. complete physical examination, height, weight, vital signs, WHO performance status, hematology, blood chemistries including coagulation and a serum lipid profile, urinalysis, CT/MRI of abdomen and pelvis, MRI/CT of brain, CT of chest (for patients with lymphangioleiomyomatosis), and ECG).

A serum pregnancy test must be completed for all female patients of child bearing potential within 28 days of Day 1 and a urine pregnancy test follow-up on Day 1 (prior to first dosing) to confirm eligibility.

The results of urine pregnancy tests will only be recorded in the patient source documents (pregnancy diary, patient records) whereas serum pregnancy test results will be recorded in the database of the assigned central lab vendor.

Prior and current concomitant medication use will also be collected and recorded.

For further details on eligibility assessments, please see [Table 7-1](#).

Baseline assessments of kidney AML

A CT/MRI assessment of the kidneys will be performed for all patients at baseline to confirm presence of at least one angiomyolipoma lesion with longest diameter ≥ 3.0 cm. The CT/MRI images will be sent to the independent radiology service for measuring of kidney tumor volume at each time point. For information regarding the scan acquisition protocol, please refer to the Independent Radiology Review Charter provided by the assigned Imaging Vendor. The presence or absence of polycystic kidney disease will also be documented by the central reviewer.

A MRI/CT of the brain will be performed at baseline to identify any SEGA lesions. These images will be centrally collected and held with no independent assessment.

7.1.3 Treatment period

Patients will receive the first dose of study drug on Day 1 and continue to be treated per protocol until documentation of angiomyolipoma progression, unacceptable toxicity, pregnancy, withdrawal of consent or investigator decision to stop the study. However, study treatment may prematurely be discontinued for other reasons as well; please refer to [Section 7.1.4](#). The maximum treatment duration is 48 weeks. Patients will visit the investigator site 4, 12, 24, and 48 weeks from Day 1 (± 7 days) and be followed as per the schedule of assessments. At these visits sufficient study drug will be dispensed to the patients to last until the next scheduled visit and unused drug will be returned to the site. Compliance will be assessed by the investigator and/or study personnel at each visit using pill counts and information provided by the patient or caregiver. This information should be captured in the source document at each visit.

7.1.4 Discontinuation of study treatment

Patients may voluntarily discontinue from the study treatment for any reason at any time. If a patient decides to discontinue from the study treatment, the investigator should make a reasonable effort (e.g. telephone, e-mail, letter) to understand the primary reason for this decision and record this information in the patient's chart and on the appropriate CRF pages. They may be considered withdrawn if they state an intention to withdraw, fail to return for visits, or become lost to follow-up for any other reason.

The investigator may discontinue study treatment for a given patient if, he/she believes that continuation would be detrimental to the patient's well-being.

In addition to mandatory discontinuation reasons for study treatment listed in [Section 6.2](#), study treatment **must** also be discontinued under the following circumstances:

- Pregnancy
- Death
- Subject/Guardian decision
- Adjustments to study treatment due to toxicity that result in treatment discontinuation (see [Section 6.2](#))
- Any other protocol deviation that results in a significant risk to the patient's safety.

Patients who discontinue study treatment should NOT be considered withdrawn from the study. They should return for the assessments indicated in [Section 7.2.1](#). If they fail to return for these assessments for unknown reasons, every effort (e.g. telephone, email, letter) should be made to contact them as specified in [Section 7.1.7](#).

For patients who discontinue treatment for reasons other than documented disease progression, death, lost to follow-up, or withdrawal of consent, kidney lesion assessments must continue to be performed as per the schedule of assessments until documented disease progression (per independent radiology review), death, lost to follow-up, or withdrawal of consent.

7.1.4.1 Replacement policy

Not applicable.

7.1.5 Withdrawal of consent

Subjects may voluntarily withdraw consent to participate in the study for any reason at any time. Withdrawal of consent occurs only when a subject:

- Does not want to participate in the study anymore, and
- Does not allow further collection of personal data

In this situation, the investigator should make a reasonable effort (e.g. telephone, e-mail, letter) to understand the primary reason for the subject's decision to withdraw his/her consent and record this information.

Study treatment must be discontinued and no further assessments conducted, and the data that would have been collected at subsequent visits will be considered missing.

Further attempts to contact the subject are not allowed unless safety findings require communicating or follow-up.

All efforts should be made to complete the assessments prior to study withdrawal. A final evaluation at the time of the subject's study withdrawal should be made as detailed in the assessment table.

Novartis will continue to keep and use collected study information (including any data resulting from the analysis of a subject's samples until their time of withdrawal) according to applicable law.

All biological samples not yet analyzed at the time of withdrawal will no longer be used, unless permitted by applicable law. They will be stored according to applicable legal requirements.

7.1.6 Follow up for safety evaluations

All patients must have safety evaluations for 30 days after the last dose of study treatment. Safety information can be collected during a visit to the site or per telephone.

Data collected should be added to the Adverse Events CRF and the Concomitant Medications CRF.

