Other tests that will be conducted routinely include laboratory tests for safety, physical examinations, vital signs, and WHO performance status. In addition, for LAM patients, pulmonary function tests will be carried out at 12, 24, 48 weeks, in the open-label treatment phase. Patients with skin lesions will have digital photos of their skin lesions taken at 12, 24, and 48 weeks, in the open-label treatment phase. A complete list of evaluations can be found in [Table 7-1](#). If unforeseen circumstances (i.e., unexpected personal reasons) prevent the patient from complying with the established visit schedule, the site can re-schedule the visit within the prescribed visit window as noted in [Table 7-1](#). The reason(s) for any visit or treatment delays will be documented for the appropriate visit.

All female patients of child bearing potential should perform urine pregnancy tests at home every 4 weeks \pm 7 days from Day 1 to end of treatment (EOT), and enter the result in the pregnancy diary.

Every patient will have end of treatment (EOT) visit within 28 days after last dose. Laboratory tests and imaging will be done at the EOT visit as described in [Table 7-1](#). Laboratory tests that were done within 1 week and imaging that was done within 8 weeks don't have to be repeated at EOT.

All patients will have a safety follow-up visit 30 days after last dose to capture AEs and SAEs that may have occurred after EOT.

Treatment Discontinuation Follow-up phase

Patients without angiomyolipoma progression at the time of early discontinuation of study treatment will enter the Treatment Discontinuation follow-up phase and will be followed with CT/MRI tumor assessments 12, 24 and 48 weeks after Day1, until eventual angiomyolipoma progression, the start of any non-study systemic anti-angiomyolipoma therapy, or withdrawal of consent, whichever occurs first. Patients with SEGA lesions should be followed for routine follow-up with brain MRI/CT scans 12, 24 and 48 weeks after Day1. During this follow up period, the site will continue to send CT/MRIs for central review, and use of non-study systemic anti-angiomyolipoma therapies will be recorded in CRF. Patients with skin lesions will also be followed with digital photography during Treatment Discontinuation follow-up phase.

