- neither kidney increases in volume by more than 20% from nadir (where nadir is the lowest kidney volume obtained for the patient, separately for each kidney, previously in the trial including screening)
- the patient does not have any angiomyolipoma-related bleeding of grade ≥ 2 (as defined by NCI CTCAE, version 4.03).

Angiomyolipoma progression will be defined as one or more of the following:

- an increase from nadir of 25% or more in angiomyolipoma volume to a value greater than screening (where angiomyolipoma volume is the sum of the volumes of all target

angiomyolipoma identified at screening and where nadir is the lowest angiomyolipoma volume achieved by the patient previously in the trial (including screening))

- the appearance of a new angiomyolipoma ≥ 1.0 cm in longest diameter
- an increase from nadir of 20% or more in the volume of either kidney to a value greater than screening, where nadir is the lowest kidney volume obtained for the patient, separately for each kidney, previously in the trial (including screening)
- angiomyolipoma-related bleeding grade ≥ 2 as defined by NCI CTCAE, version 4.03.

Note: In some instances, disease that is measurable as a target lesion at screening and appears to be one mass can split to become two or more smaller sub-lesions. When this occurs, the image review system allows the central reviewer to identify the separate sub-lesions as unique and non-overlapping so that the volume of each sub-lesion can be determined. The combined volumes of the sub-lesions will be reported as the volume of the lesion that has split. The individual split lesions will not be considered as new lesions, and will not automatically trigger an angiomyolipoma progression.

Conversely, it is also possible that two or more lesions which were distinctly separate at screening become confluent at subsequent visits. The central reviewer will be required to separate the confluent mass into regions relating to the original several distinct lesions. These regions will continue to be measured as separate lesions. Although this raises the possibility of increased variability in the measurements of the individual lesions due to the lack of distinct borders within the confluent mass, the primary endpoint (sum of lesion volumes) will still be accurately measured so long as the confluent mass itself has distinguishable borders.

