8.2.2 Reporting

To ensure patient safety, every SAE, regardless of suspected causality, occurring after the patient has provided informed consent and until at least 30 days after the patient has stopped study treatment must be reported to Novartis within 24 hours of learning of its occurrence.

Any additional information for the SAE including complications, progression of the initial SAE, and recurrent episodes must be reported as follow-up to the original episode within 24 hours of the investigator receiving the follow-up information. An SAE occurring at a different time interval or otherwise considered completely unrelated to a previously reported one should be reported separately as a new event.

Any SAEs experienced after the 30 day safety evaluation follow-up period should only be reported to Novartis if the investigator suspects a causal relationship to the study treatment.

Information about all SAEs is collected and recorded on the Serious Adverse Event Report Form; all applicable sections of the form must be completed in order to provide a clinically thorough report. The investigator must assess and record the relationship of each SAE to study treatment, complete the SAE Report Form in English, and submit the completed form within 24 hours to Novartis. Detailed instructions regarding the SAE submission process and requirements for signatures are to be found in the investigator folder provided to each site

Each re-occurrence, complication, or progression of the original event should be reported as a follow-up to that event regardless of when it occurs. The follow-up information should

describe whether the event has resolved or continues, if and how it was treated, whether the blind was broken or not, and whether the patient continued or withdrew from study participation.

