10.5.1 Angiomyolipoma response rate

Angiomyolipoma response rate, is defined as the proportion of patients with an angiomyolipoma response, as defined in [Section 7.2.1.1](#), using data from the Independent Central Radiology Review of CT/MRIs and the Adverse Events CRF page (to identify angiomyolipoma-related bleeding of grade 2 or worse as defined by NCI CTCAE version 4.03).

Angiomyolipoma response rate will be calculated based on the FAS and presented together with its 95% confidence interval for all patients.

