Angiomyolipoma progression, is defined as the proportion of patients with an angiomyolipoma progression during maximum treatment duration of 48 weeks, as defined as above, using data from the Independent Central Radiology Review of CT/MRIs and the Adverse Events CRF page (to identify angiomyolipoma-related bleeding of grade 2 or worse as defined by NCI CTCAE version 4.03).

Angiomyolipoma progression rate will be calculated based on the FAS and presented together with an exact 95% confidence interval for all patients.

Time to angiomyolipoma progression

Time to angiomyolipoma progression (TTAP) is defined as the time from the start date of everolimus to the date of the first documented angiomyolipoma progression, where angiomyolipoma progression is defined as above. TTAP will be censored if angiomyolipoma progression is not observed before the first to occur out of

- (i) the cut-off date for the analysis, or
- (ii) the date when a further systemic anti-angiomyolipoma medication is started, or
- (iii) the date of a angiomyolipoma-related surgery or
- (iv) the date of death.

The censoring date will be the date of the last adequate CT/MRI assessment occurring before the first of any of these four events to have occurred, or treatment day 1 if there were no adequate CT/MRI assessments performed post-baseline.

TTAP will be presented in months and is calculated as:

$$(\text{Date of angiomyolipoma progression/censoring} - \text{Start date of everolimus} + 1) \times 12 \div 365.25.$$

The TTAP distribution will be presented descriptively in the FAS using a Kaplan-Meier curve. Summary statistics from the Kaplan-Meier distribution will be determined, including the

median TTAP and the proportions of patients remaining progression-free at 3, 6, and 12 months. These statistics will be given as point estimates with 95% confidence intervals.

Per protocol, tumor assessment was done at Week 4, 12, 24 and 48. At database lock, it was observed that most patients were censored at treatment completion at the time of their Week 48 assessment, and only 3 out of the 40 patients had angiomyolipoma progression observed. 9 patients were discovered to have TTAP greater than the maximum treatment duration of 48 weeks + 7 day window, among which one patient had progressed; this patient had the longest TTAP in the analysis set.

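### AML-related bleeding counts toward progression up to Week 48, but for patients who stop early its recording is not scheduled beyond 30 days after the last dose

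*Protocol*

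**What the plan says.** **Endpoint.** Protocol 7.2.1.1 lists "angiomyolipoma-related bleeding grade ≥ 2 as defined by NCI CTCAE, version 4.03" as sufficient for progression, and makes it a condition of response that "the patient does not have any angiomyolipoma-related bleeding of grade ≥ 2". SAP 2.7.1 repeats both. Every other component is read from scans by central review. For bleeding, Protocol 10.5.1 names as source "the Adverse Events CRF page (to identify angiomyolipoma-related bleeding of grade 2 or worse as defined by NCI CTCAE version 4.03"; SAP 2.7.1 names the same page and adds a clinical review of what investigators reported there.

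**Window.** Under Protocol 4.1 and 7.2.1, patients who stop early without progression keep having kidney scans at Weeks 12, 24 and 48 from Day 1. The final analysis waits for this follow-up (Protocol 10.7, SAP 2.14). In the SAP, "Angiomyolipoma progression rate will be calculated based on the FAS", with an exact interval, and time to AML progression (TTAP) is not censored when treatment stops.

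**Capture after stopping.** Protocol 7.1.6 states: "All patients must have safety evaluations for 30 days after the last dose of study treatment". In Table 7-1 the adverse event and SAE rows end at the safety follow-up visit. The efficacy follow-up column carries imaging, skin photographs, disposition and later antineoplastic therapy, but no AE or SAE mark. For the same phase Section 4.1 says "the site will continue to send CT/MRIs for central review, and use of non-study systemic anti-angiomyolipoma therapies will be recorded in CRF", and does not mention bleeding. Section 8.2.2 adds: "Any SAEs experienced after the 30 day safety evaluation follow-up period should only be reported to Novartis if the investigator suspects a causal relationship".

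**Text pointing the other way.** Sections 7.1 and 8.1.1 make 30 days a minimum. Section 7.2.2 has adverse events collected at every visit, and Section 8.1.1 has them sought at each study visit.

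**The concern.** One component of progression depends on AE reporting, and the visit schedule drops AE reporting while the progression clock is still running. A site that follows Table 7-1 would send the follow-up scan and have no prompt to record a bleed. A tumour bleed off drug might well not be judged drug-related, in which case Section 8.2.2 would not bring it in as an SAE either. A site that follows Sections 7.2.2 and 8.1.1 would ask and record.

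If a bleed goes unrecorded, the patient is scored from scans alone and may count as stable or progression-free. For the progression rate and TTAP the error can only run in the favourable direction. The protocol's background gives reason to take this seriously: it links lesion size to hemorrhage (Section 1.1) and reports regrowth after everolimus is stopped (Sections 1.1 and 1.2.3). It also says that volumes did not return to pre-treatment values, so this is plausibility and not evidence of a raised bleeding rate within 48 weeks.

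**Working it through.** **Check of method.** The SAP's exact (Clopper-Pearson) interval for 33/79 gives 30.8% to 53.4%, the interval stated in Protocol 2.1. For 65/112 it gives 48.3% to 67.3%, as in Protocol 1.1. The plan states no power, alpha or event target to reproduce; about 40 patients is a feasibility number.

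**Who is exposed.** Week 48 is Day 336 in SAP Table 2.1-1. With last dose at the end of week w, the days without scheduled AE capture are 336 − (7w + 30), or zero if negative.

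| Last dose | Uncovered days to Day 336 |
|---|---|
| Week 4 | 336 − 58 = 278 |
| Week 12 | 336 − 114 = 222 |
| Week 24 | 336 − 198 = 138 |
| Week 36 | 336 − 282 = 54 |
| Week 44 | 336 − 338 < 0, so 0 |

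The gap closes at w = (336 − 30)/7 = 43.7. Counting to Day 343, the end of the Week 48 window, it closes at (343 − 30)/7 = 44.7. So only patients with a last dose before about Week 44 are affected, and completers are not.

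**How many.** The documents do not say. Amendment 2 (06-Dec-2019) states that all 40 patients were then on treatment, so the count was zero at that date.

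**Expected missed bleeds (assumed inputs).** For D early discontinuers, yearly off-drug bleed rate r and gap g in days, the expected number is D × [1 − (1 − r)^(g/365.25)]. D and r are assumptions; stopping is taken at Week 12 or 24.

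- D = 4, r = 1%, g = 138: 4 × 0.0038 = 0.015; chance of at least one, 1.5%.
- D = 4, r = 10%, g = 222: 4 × 0.062 = 0.248; chance of at least one, 23%.
- D = 8, over the same range: 0.03 to 0.50; chance of at least one, 3% to 40%.

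On these assumptions the likely number is zero or one patient.

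**Effect of one.** SAP 2.7.1 reports 3 progressions in 40 patients. Each recovered bleed in a patient not already counted adds 1/40 = 2.5 points.

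| Progressions | Rate | Exact 95% CI |
|---|---|---|
| 3/40 | 7.5% | 1.6 to 20.4 |
| 4/40 | 10.0% | 2.8 to 23.7 |

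One of the three progressions came after 48 weeks + 7 days, and the SAP does not say whether the 48-week rate counts it. The illustration uses 3.

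**Response.** Under SAP 2.7.1, best overall response is the best status before progression, so a bleed after a documented response does not undo it. A false responder would need an unrecorded bleed more than 30 days off drug, followed by a first reduction of at least 50% on a later off-drug scan. With regrowth off drug expected, that is very unlikely.

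**The case against.** The strongest reply is that the protocol does not end AE collection at 30 days. Sections 7.1 and 8.1.1 set a minimum. Sections 7.2.2 and 8.1.1 tie AE enquiry to every visit, the efficacy follow-up visits are numbered study visits, and Section 7.1.4 says that stopping treatment is not withdrawal from the study. Protocol 10.4.1 and 10.4.2 and SAP 2.8.1 foresee and flag later AEs, and the SAP's 30-day limit governs safety tables, not the derivation of progression. Suspected progression at any time calls for examination and imaging. This stands as far as it goes: later capture is permitted and may have happened. But the schedule does not ask for it, and an examination kept in source documents plus a scan does not create an AE record. An endpoint component needs uniform, required recording.

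It is also fair that progression is an other-secondary, descriptive endpoint with no hypothesis test. Protocol 10.5.2 only lists and narrates such patients; the rate and TTAP come from the SAP.

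Three stronger readings are tempting, and the documents do not support them:

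- A reader might infer that AE collection stops, so bleeds were missed and progression is under-counted. No document shows a missed bleed.
- A reader might infer an over-stated response rate. The best-response rule above leaves almost no room for that.
- A reader might apply the pivotal study's discontinuation for AEs, 10/112, to get 40 × 10/112 = 3.6 affected patients. That figure comes from a study with median follow-up of 47.2 months, not 48 weeks, and discontinuers have not thereby bled.

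**Conclusion.** The point holds as a conflict between passages with a possible one-directional effect. The endpoint runs to Week 48, and the only named source for its bleeding component has no scheduled collection beyond 30 days after the last dose, while other sections imply that collection goes on. Capture in early discontinuers may therefore be incomplete or vary by site, and the progression rate and TTAP may look better than they are.

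The size is probably zero or one patient. This rests on assumed numbers of discontinuers and assumed bleed rates, because the documents give neither. One patient would not change the overall picture: the two intervals above overlap almost entirely. With only three events, however, it would be a one-third relative increase. The SAP's statement that Kaplan-Meier estimates up to 48 weeks are fully valid needs this qualification until the number of exposed patients is known. The remedy is cheap enough to be worth making.

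**What to change.** Reconcile Table 7-1 and Sections 7.1.6 and 8.2.2 with Sections 7.1, 7.2.2 and 8.1.1. Require AML-related bleeding, with date and CTCAE grade and regardless of causality, to be recorded on the Adverse Events CRF at the existing Week 12, 24 and 48 efficacy follow-up visits, until progression or Week 48.

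If data collection is closed, as the SAP's reference to database lock suggests:

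1. Count the patients whose last dose was before about Week 44 and report their uncovered days.
2. Query their source records for such bleeds before the final analysis. Show any that are found in a sensitivity analysis of the progression rate and TTAP.
3. If this cannot be done, state in SAP 2.7.1 that progression later than 30 days after the last dose is essentially radiological only, and give the number of patients concerned. If there are none, one sentence settles the matter.

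**Cost.** Prospectively, one question and one table mark at visits already planned for the scan, with a small data-entry burden and no extra procedure. Retrospectively, a source query for what is probably a handful of patients. Entering the findings in a locked database would need the written agreement described in Protocol 9.4; reporting them as a sensitivity analysis outside it would not.
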